5.1.2 Treatment Period

5.1.2.1 Day 0, Surgery (Intra-operative)

The following evaluations will be performed in the OR, during surgery:

- Collection of CPB data, including the following:
 - Equipment type
 - Cardioplegia solution type
 - Composition of isovolumetric exchange fluid for ultrafiltration and/or modified ultrafiltration
 - Exchange volumes in and out
 - Documentation of L-citrulline or placebo administration
 - CPB start and end times and decannulation time
- Hemodynamic monitoring, including the following:
 - Heart rate
 - Systemic blood pressure (BP)
 - O₂ saturation
 - Central Venous Pressure (CVP) measurements
 - Pulmonary Artery Pressure (PAP) measurements (if PA line is placed)

Baseline values are first recorded in the OR by Anesthesia. Results will be monitored during surgery according to the Institution's standard of care, but results will only be recorded approximately every 15 minutes.

- Arterial Blood Gases (ABGs)
 - PaO₂, PaCO₂, HCO₃, and pH measurements
 - Baseline values are first recorded in the OR by Anesthesia. All results obtained after induction of anesthesia and during surgery will be recorded.
- Bolus of L-citrulline at 150 mg/kg or placebo at initiation of CPB; addition of L-citrulline at a concentration of 200 µmol/L or placebo given as a bolus during bypass.
 This may be administered as a one-time bolus or multiple administrations to compensate for fluids containing L-citrulline that may be removed from the patient

during the course of the operation and thus to maintain the concentration of 200 µmol/L. The total dose will be dependent upon the total amount of any volume administered and removed during CPB.

- Blood draw (10 minutes after study drug is administered):
 - serum electrolytes, BUN, and creatinine
 - CBC with differential
 - ACT
 - plasma L-citrulline (1.0 mL)
- Inotrope and other concomitant medication documentation
- Adverse events documentation

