Probable Clinical events with temporal relation to the study treatment, and a

potential alternative etiology is not apparent (e.g., fever or irritability when no other symptoms suggestive of an illness are present) with a reasonable time relationship to IMP administration, and is unlikely to

be attributed to concurrent disease or other drugs or chemicals.

Definite Clinical events with plausible temporal relationship to IMP

administration, and that cannot be explained by concurrent disease or other drugs or chemicals; events which have a timely relation to the study and no alternative etiology is present. They must have occurred within a reasonable temporal sequence of the treatment, must be reasonably explained and must follow a known pattern of response.

Action Taken

The investigator will describe the action taken in the appropriate section of the CRF, as follows:

- None
- IMP stopped
- IMP temporarily interrupted
- Concomitant medication
- Other, specify

"Expected" Adverse Events

"Expected" adverse events are those AE's that are associated with the condition or the treatment and are listed as such in the trial protocol and/or the Investigator Brochure, whether or not they occur in every case.

Congenital heart surgery and events associated with the surgery are considered "expected" in many participants as part of the underlying disease of study and therefore not necessarily reportable to the IRB as adverse events. A compilation of these AE's is in **Table 1**.

Table 1: Adverse Events Associated with Pediatric Congenital Heart Defect Surgery

Surgical	HCT < 20
Bleeding > 10 cc/kg/hr x 2 hours	INR >2.0
Chest re-exploration	Electrolyte
Respiratory:	K <2.5 (not due to lasix)
Reintubation	Na <125
Pleural effusion requiring chest tube	iCa<4.0
Pneumothorax	Mg < 1.5
Pulmonary embolus	Glucose <50
Cardiac	Neurologic
Ventricular tachycardia	IVH
Supraventricular tachycardia	Seizures
Junctional ectopic tachycardia	Renal
Atrial fibrillation	BUN >40
Cardioversion	Creat > 1.5
ID:	Need for CVVH or dialysis
Fever > 38.5	Medications
Nosocomial blood stream infection	Epi bolus in non code situation
(utilizing NNIS criteria)	Atropine bolus in non code situation
Nosocomial pneumonia (utilizing NNIS	Vasopressin infusion
criteria)	Amiodarone infusion
Nosocomial urinary tract infection	General
(utilizing NNIS criteria)	PCCU readmission
Surgical wound infection (utilizing	
NNIS criteria)	
Hematologic	
WBC<5	
PLT <50K	

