The number of subjects with any refractory hypotension from end of surgery until 48 hours will be compared between groups using Fishers' exact test. Additionally, a logistic regression analysis will be applied including factors treatment and site.

Hypotension assessment (Refractory hypotension is defined as a 20% drop of MAP below specific age-related criteria (Haque and Zaritsky (2007) for greater than 30 minutes):

- Infants: MAP of 40
- Age 1 year: MAP of 40
- Age 2 years: MAP of 44
- Age 3 years: MAP of 47
- Age 4 years: MAP of 52
- Age 6 years: MAP of 53
- Age 7 years: MAP of 52
- Age 8 years: MAP of 54
- Age 9 years: MAP of 55
- Age 10 years: MAP of 56
- Age 11 years: MAP of 57
- Age 12 years: MAP of 58
- Age 13 years: MAP of 59
- Age 14 years: MAP of 61
- Age 15 years: MAP of 62
- Age 16 years: MAP of 63
- Age 17-18 years: MAP of 64

Laboratory values

Laboratory values will be analyzed descriptively. For quantitative parameters, absolute values as well as absolute and percentage changes from Baseline will be tabulated using summary statistics for all observed time points. For qualitative variables, frequency tables will be generated for all observed time points.

A conversion to the given standard units will be performed if necessary. Concentrations below the limit of quantification will be set to zero.

All laboratory values will be classified as normal or abnormal according to the laboratories normal ranges. Abnormal values will be indicated as clinically significant or not clinically significant by the investigator. Shift tables (normal / abnormal, not clinically significant / abnormal, clinically significant) will be created illustrating changes with respect to the laboratories normal ranges and clinical significance between Baseline and post Baseline visits Day 1, Day 2, and Day 28/ Discharge.

The following laboratory parameters were determined and will be described for the corresponding visits:

Hematology

Type of all parameters is quantitative.

- Hemoglobin
- Hematocrit
- Red blood cell (RBC) count
- White blood cell (WBC) count (total and differential)
- Platelet count

Serum Electrolytes, BUN, and creatinine

Type of all parameters is quantitative.

- Serum electrolytes (Na, K, Ca, Mg and Cl)
- BUN
- Creatinine

Liver function tests

Type of all parameters is quantitative.

- Bilirubin (total)
- AP
- AST
- ALT
- LDH

Coagulation

Type of all parameters is quantitative.

- ACT

Urinalysis

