4.7 Analysis of Other Relevant Variables

Arterial blood gases (ABG)

The number of patients with any low or high values for AGB parameters PaO₂, PaCO₂, HCO₃, pH per 6 hour time window and overall will be evaluated.

6 hour time windows from time of post-op admission to the PICU will be defined as:

- Time of AGB evaluation = Time collected AGB - Time of admission to PICU
- >0 to \leq 6 hrs (>0min to \leq 360min)
- >6 to \leq 12 hrs (>360min to \leq 720min)
- >12 to \leq 18 hrs (>720min to \leq 1080min)
- ...
- >42 to \leq 48 hrs (>2520min to \leq 2880min)
- >48 hrs (>2880min)

Normal ranges for the AGB parameters are defined as:

- PaO₂: <70 mmHg = low; 70-100 mmHg = normal; >100 mmHg = high
- PaCO₂: <35 mmHg = low; 35-45 mmHg = normal; >45 mmHg = high
- HCO₃: <22 mmol/L = low; 22-26 mmol/L = normal; >26 mmol/L = high
- pH: <7.35 = low; 7.35-7.45 = normal; >7.45 = high

Patients will be categorized per AGB parameter and per time window (and overall) as follows:

- Low: At least one value at one visit was low
- Normal: All values at all visit were normal
- High: At least one value at one visit was high
- Low/High: At least one value at one visit was low, and at least one value at one visit was high

The number of patients for those categories will be tabulated per AGB parameter and per time window (and overall).

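### The SAP's laboratory shift tables carry no low/high direction, so no planned laboratory table counts which way children leave their normal range

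*SAP*

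**What the plan says.** SAP 4.5, under laboratory values, sets the classification in three steps.

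- Range: "All laboratory values will be classified as normal or abnormal according to the laboratories normal ranges".
- Rating: "Abnormal values will be indicated as clinically significant or not clinically significant by the investigator".
- Table: "Shift tables (normal / abnormal, not clinically significant / abnormal, clinically significant) will be created", comparing status "between Baseline and post Baseline visits Day 1, Day 2, and Day 28/ Discharge".

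The rule therefore has three classes: normal, abnormal NCS and abnormal CS. None records the side of the range on which a value lies.

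Other planned outputs bear on the point:

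- SAP 4.5 and Protocol 7.1.5 tabulate quantitative laboratory values and their signed changes from Baseline, absolute and in percent, at every time point with data. SAP section 4 says such summaries include mean, SD, median, quartiles and extremes.
- Protocol 6.2.2.1 makes clinically significant abnormal laboratory results adverse events. SAP 4.5 reports adverse events by preferred term with numbers of affected subjects. Terms reaching 5% in either arm also get a relative risk, risk difference and odds ratio.
- SAP 4.7 does keep direction for blood gases, for example "pH: <7.35 = low; 7.35-7.45 = normal; >7.45 = high", and has a category for a patient with both low and high values.
- No statistical test is planned on laboratory values.

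**The concern.** Sodium, potassium, calcium, magnesium, chloride, white cells, hemoglobin and platelets can all be abnormal on either side. A shift table is meant to show how many children moved out of range and how. Here it shows how many moved but not which way.

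Two consequences follow. A child who goes from low to high with the same rating at both visits sits on the diagonal and is read as unchanged. And an effect that lowers a parameter in one arm cannot be told, in the shift table, from one that raises it in the other, if the counts agree within each rating.

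Change in laboratory values is a named safety endpoint (Protocol 3.2.2). Since it is not tested, its assessment rests on these descriptive tables. The testing is local, with each laboratory supplying its own ranges (Protocol 6.2.2.2), across about 28 sites and ages up to 18 years. Pooled mean changes therefore cannot show which children left their own range. The shift table is the output built for that purpose.

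**Working it through.** The documents give no figure on this point, so there is none to reproduce. The check applies the SAP's three-class rule and a five-class directional rule to the same data.

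**Counting the cells.**

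- With direction and rating there are 5 classes, so 5 × 5 = 25 Baseline-to-visit cells. The SAP's rule has 3 × 3 = 9.
- Low/high swings: 2 ratings at Baseline × 2 ratings at the visit × 2 directions = 8.
- Swings with the same rating at both visits: 2 ratings × 2 directions = 4. These fall on the SAP's diagonal.
- The other 4 appear as a change between NCS and CS, so a shift is visible but its reversal of direction is not.

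**Two arms with opposite effects.** These inputs are assumptions, not from the documents: reference range 3.5 to 5.0, every Baseline value 4.25, and the ratings shown. The 95 children per arm is the planned number randomized.

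| | Arm A | Arm B |
|---|---|---|
| Unchanged at 4.25 | 70 | 70 |
| Moved, rated NCS | 20, to 3.2 | 20, to 5.3 |
| Moved, rated CS | 5, to 2.8 | 5, to 5.7 |
| SAP shift table: normal to normal / NCS / CS | 70 / 20 / 5 | 70 / 20 / 5 |
| Five-class table | 20 normal to low NCS, 5 normal to low CS | 20 normal to high NCS, 5 normal to high CS |
| Mean change | (20 × −1.05 + 5 × −1.45)/95 = −28.25/95 = −0.30 | +28.25/95 = +0.30 |
| SD of change | 0.51 | 0.51 |
| Minimum, maximum change | −1.45, 0 | 0, +1.45 |

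The SAP's shift tables are identical. The five-class tables differ, and so do the planned change summaries.

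**A single child.** A move from 3.2 to 5.3, both NCS, is NCS to NCS under the SAP (no shift) and low NCS to high NCS under five classes. A move from 3.2 (NCS) to 5.7 (CS) does show under the SAP, as NCS to CS.

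**An arm with movement both ways.** Take 71 unchanged, 12 falling to 3.2 and 12 rising to 5.3, all NCS.

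- Mean change = (12 × −1.05 + 12 × 1.05)/95 = 0. Median and both quartiles are also 0.
- Only the SD and the extremes (−1.05, +1.05) show movement.
- The SAP's shift table reads 71 normal to normal and 24 normal to NCS. An arm in which all 24 fell gives the same table, with mean change 24 × −1.05/95 = −0.27.

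The summaries tell these two arms apart, but neither output gives the split of 12 and 12.

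**What the adverse event tables pick up.** In arm A the 5 children rated CS are 5/95 = 5.3%. They would reach the 5% listing if all were reported and coded to one preferred term. The 20 rated NCS (20/95 = 21.1%) are not laboratory adverse events under the protocol's definition and are counted only in the shift table, without direction.

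**The case against.** The strongest reply is that direction is reported elsewhere. The signed summaries in the same SAP paragraph would show opposite effects as opposite signs. Clinically significant abnormalities are counted as adverse events by named term, with risk differences for the commoner ones. The laboratory analysis is descriptive, Protocol 7.1.5 requires no shift table, and Appendix A, which lists the tables, was not in the text available, so its shells might add direction.

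Most of this stands and limits the point. It does not remove it. The summaries give averages and extremes rather than counts against each laboratory's range, and the adverse event route leaves out values rated NCS.

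Several stronger readings are tempting, and the documents do not support them:

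- A reader might infer that there is a single abnormal class. There are two; what both lack is direction.
- A reader might infer that every low/high swing is hidden, or that opposite effects always match. Each holds only under the stated condition on the ratings.
- A reader might infer that no other output counts affected children. The adverse event tables do so for clinically significant values.
- A reader might see a contradiction with SAP 4.7. That is a different type of table, with fixed ranges and no rating. It shows only that the authors found direction worth keeping for blood gases.
- A reader might conclude that the intra-operative sample ("Blood draw (10 minutes after study drug is administered") is lost because the shift tables start at Day 1. It is covered by the summaries. It is drawn while bypass fluids are being exchanged, so leaving it out of a shift table is defensible.

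**Conclusion.** The concern holds in a limited form. As written, SAP 4.5 shift tables cannot show direction. Low/high swings with an unchanged rating (4 of 8 kinds) read as no shift, and opposite effects give identical shift tables when the NCS and CS counts match. What the plan lacks is a count, by direction, of children who leave their laboratory's normal range, mainly those rated NCS.

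The severity is minor: no hypothesis test, endpoint or sample size is affected. The numerical example rests on assumed values and shows only what the rule can hide; it does not predict the trial's data. The conclusion also assumes that Appendix A follows the SAP text. If its shells already separate low from high, the SAP sentence only needs to say so.

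**What to change.** In SAP 4.5, for quantitative laboratory parameters only, replace the three shift classes with five: low CS, low NCS, normal, high NCS and high CS. Base low and high on the same laboratory ranges that already decide normal or abnormal. Keep the present classes for the qualitative urinalysis items (color, casts, bacteria and the like), where low and high have no meaning. Keep the visits as planned.

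The cost is one changed SAP sentence, reprogramming of one table type, and larger, sparser tables (25 cells instead of 9 per parameter and visit). No new measurements are needed if the numeric limits, or a low/high flag, are in the database. The documents say that laboratories supply the ranges but not how they are stored, so data management should confirm this first. The change should be fixed before unblinding.

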4.6 Analysis of Exploratory Variables

PF ratio

PF ratio is defined as PaO₂ [mmHg] divided by FiO₂ in [%]. PaO₂ and FiO₂ are measured at varying times. Since FiO₂ is measured more often, PF ratio will only be calculated for the times when a corresponding PaO₂ measurement is available (defined as FiO₂ value measured at time of PaO₂ value \pm 0.5h). As denominator, the FiO₂ value measured with minimum time difference will be used. If there is no FiO₂ value measured at time of PaO₂ \pm 0.5h, no PF ratio will be calculated.

The PF ratio will be listed. In addition, the mean PF ratio per patient and visit will be calculated and displayed using basic statistics.

Example:

ID	Date/time of FiO2	FiO2 value
1	2018-01-08T11:57	100
2	2018-01-08T13:43	80
3	2018-01-08T14:00	80
4	2018-01-08T14:43	80
5	2018-01-08T15:00	70
6	2018-01-08T17:11	75
7	2018-01-08T18:00	75
8	2018-01-08T19:00	75
9	2018-01-08T20:18	75
10	2018-01-08T23:33	75

Date/time of PaO2	PaO2 value	PF ratio	ID of matched FiO2
2018-01-08T11:15	73	no matching value	
2018-01-08T12:32	236	no matching value	
2018-01-08T14:49	267	267/80	4
2018-01-08T16:50	147	147/75	6
2018-01-08T17:59	213	213/75	7
2018-01-08T19:04	273	273/75	8
2018-01-08T20:15	326	326/75	9
2018-01-08T22:27	336	no matching value	

28-day mortality

The percentage of patients who have died at Day 28 will be presented by treatment group.

4.7 Analysis of Other Relevant Variables

Arterial blood gases (ABG)

The number of patients with any low or high values for AGB parameters PaO₂, PaCO₂, HCO₃, pH per 6 hour time window and overall will be evaluated.

6 hour time windows from time of post-op admission to the PICU will be defined as:

- Time of AGB evaluation = Time collected AGB - Time of admission to PICU
- >0 to \leq 6 hrs (>0min to \leq 360min)
- >6 to \leq 12 hrs (>360min to \leq 720min)
- >12 to \leq 18 hrs (>720min to \leq 1080min)
- ...
- >42 to \leq 48 hrs (>2520min to \leq 2880min)
- >48 hrs (>2880min)

Normal ranges for the AGB parameters are defined as:

- PaO₂: <70 mmHg = low; 70-100 mmHg = normal; >100 mmHg = high
- PaCO₂: <35 mmHg = low; 35-45 mmHg = normal; >45 mmHg = high
- HCO₃: <22 mmol/L = low; 22-26 mmol/L = normal; >26 mmol/L = high
- pH: <7.35 = low; 7.35-7.45 = normal; >7.45 = high

Patients will be categorized per AGB parameter and per time window (and overall) as follows:

- Low: At least one value at one visit was low
- Normal: All values at all visit were normal
- High: At least one value at one visit was high
- Low/High: At least one value at one visit was low, and at least one value at one visit was high

The number of patients for those categories will be tabulated per AGB parameter and per time window (and overall).

4.8 Missing Values

Efficacy endpoints describing length of time

If a subject did not receive any mechanical ventilation / inotropes / positive pressure ventilation / intubation / vasodilators / chest tube, the corresponding length of time is set to 0. For subjects who died before discharge from the hospital or before Day 28, respectively, the observed length of time will be used for analysis of all time variables.

For time to event analyses censoring information will be used for statistical analyses.

No other imputation of missing values will be used.

Efficacy endpoint inotrope score

The total inotrope score will be set to zero after the bypass pump has been removed. It will also be set to zero for patients not using inotropes at all.

Further secondary efficacy endpoints

No imputation of missing values will be applied for the secondary endpoints hemodynamic improvement, volume of chest tube drainage, and L-citrulline plasma levels.

Safety endpoints

For laboratory data, concentrations below the limit of quantification will be set to zero. Missing safety data or safety assessments will not be estimated nor imputed. All safety summaries and analyses will be based on observed data.

No other imputation of missing values will be used.

4.9 Data Base Closure and Data Review

The statistical analysis of the clinical observation period will be performed after cleaning and database lock of all data and final unblinding.

A blind data review meeting (BDRM) will be conducted based on all data to check for protocol deviations and to allocate the subjects to the analysis sets FAS, mFAS, SAF, and PP. These evaluations and assessments will be done together and in agreement with the Sponsor, however FGK will provide the Sponsor with the appropriate subject listings. BDRM will be done via WebEx.

Data unblinding on the basis of the randomization listing and the analysis will be done after BDRM has been conducted and BDRM minutes have been signed by both the Sponsor and FGK.

4.10 Miscellaneous

For qualitative variables the frequencies (absolute and relative) are calculated. If no further remark is given in the description of the tables following format will be used for all tables with qualitative variables:

		Y-variable(s) (e.g., treatment group)					
		Category 1		Category 2		Total	
X-variable(s)		N	%	N	%	N	%
category 1	xx	xx.x	xx	xx.x	xx	xx	xx.x
category 2	xx	xx.x	xx	xx.x	xx	xx	xx.x
Missing	xx	xx.x	xx	xx.x	xx	xx	xx.x
Total	xx	100.0	xx	100.0	xx	xx	100.0

For this standard format the description of the tables in Appendix A determines only the X- and Y-variables. If another format of table is described in the details to the tables, the real design will be determined by the technical possibilities within SAS and may not look identical to the provided example. However, all information as displayed will be included.

Quantitative parameters will be described by declaring the mean value, standard deviation, minimum, first quartile, median, third quartile, and maximum. In the description of the tables this will be denoted by „basic statistics“.

The listings are always sorted by treatment group, center, and subject. If a different sorting order should be used for some listings this will be remarked separately. The variables for the special listings are explicitly given in the description of listings. All listings will be presented for the full analysis set, if not stated differently. Indicator variables for further analysis sets, e.g., safety analysis set, will be added to listing “Disposition of subjects and analysis sets”.

The following title will be used for all generated tables, listings, and graphs:

CIT-003-01: L-CITRULLINE

Page # of #

<Subtitle for description of contents - if applicable>

<Analysis set>

The numbering NNN of the tables/listings/graphs will be stated in the detailed description (Appendix A).

Following footnote will be used for all generated tables, listings, and graphs:

Date: <Actual date>

Program: <Name of program>

The statistical evaluation will be performed using SAS version 9.3 or higher.

5 Changes from Protocol

Length of time of inotrope therapy

According to protocol length of time of inotrope use will be measured until the subject is discharged from the hospital or until Day 28, whichever occurs first. The length will be derived as the time of first use until last use (in hours).

Actually the exact start and end date/times of inotropes will be documented in the CRF, therefore the length of time of inotrope use will be derived in minutes.

Additionally, to be consistent to the time of mechanical ventilation, the time of separation from CPB will be used as starting point instead of time of first use.

Also, it is stated "For any missing scores between two non-missing scores they will be imputed using the most recent non-missing score (the last observation carried forward principle)." Due to the inotrope documentation as described above the LOCF principle is not to be applied.

6 Literature

n/a

7 Appendices

- Appendix A: List of generated summary tables, listings, and graphs

8 Signatures**Statistician:**

[name]
FGK Clinical Research GmbH
[name]
[name]
Germany

04 Oct 2018

Date (ddmmmyyyy)

[name]

Signature

Sponsor:

[name]
Aklepion Pharmaceuticals, LLC
Chief Medical Officer
[name]
[name]

02 Oct 2018

Date (ddmmmyyyy)

[name]

Signature

[name], BA
Aklepion Pharmaceuticals, LLC
Director of Clinical Operations
[name]
[name]

02 October, 2018

Date (ddmmmyyyy)

[name]

Signature
